6.2.5 Primary Efficacy and Safety evaluation

6.2.5.1 Part A

The following primary safety parameters will be evaluated in **Part A** based on SAF:

- Number of patients experiencing adverse events.
- Type, incidence, and severity of treatment-related adverse events, graded according to Common Terminology Criteria for Adverse Events (CTCAE v. 4.03, 14th June 2010).

AEs will be coded using MedDRA dictionary (using the most updated version). Adverse events (AEs) will be reported on a per subject basis. If a patient has more than one AE for a treatment that coded to the same preferred term (PT), the patient will be counted only once for that preferred term. Similarly, if a patient has more than one AE for a treatment within a system organ class (SOC) category, the patient will be counted only once in that system organ class category. A patient with multiple CTCAE grades for an AE will be summarized under the maximum CTCAE grade recorded for the event.

Any Adverse Events which started at or after the first administration of study treatment will be considered a treatment Emergent Adverse Event (TEAE). If the start date is missing for an AE, the AE will be considered to be treatment emergent.

An overview of AEs including the number of subjects with at least one AE, at least one TEAE, at least one drug-related TEAE, at least one serious TEAE, any SAE, any AE leading to death, any TEAE leading to death, any TEAE leading to drug discontinuation, at least one grade ≥ 3 TEAE, will be presented. The following AE frequency tables will be also provided:

- incidence of TEAEs by primary SOC and PT;
- incidence of drug-related TEAEs by primary SOC and PT;
- incidence of TEAEs by maximum severity, primary SOC and PT;
- incidence of TEAEs by strongest relationship, maximum severity, primary SOC and PT;
- incidence of TESAEs by primary SOC and PT;
- incidence of TEAEs leading to study drug discontinuation by primary SOC and PT;
- incidence of TEAEs leading to dose modification by primary SOC and PT.

In addition, the following primary parameter will be evaluated in **Part A** based on MTD analysis set population:

- MTD of Givinostat.

6.2.5.2 Part B

The following primary efficacy parameters will be evaluated in **Part B after 3 cycles of treatment** (i.e. at the end of Cycle 3) based on ITT and PP:

- **For PV and ET (if any):** Complete response (CR) and partial response (PR) rate according to clinico-haematological ELN response criteria [21] (see [paragraph 4.6.1](#));
- **For MF (if any):** Complete response (CR), major response, moderate response and minor response rate according to the EUMNET response criteria (see [paragraph 4.6.1](#)).

Note that only in case the enrolment in **Part A** is slow (i.e. < 5 patients enrolled in 3 months, the eligibility for this part of the study may be expanded to all patients with cMPN.

The clinico-haematological ELN response criteria [21] (see [paragraph 4.6.1](#)) and EUMNET response criteria will be used to assess the preliminary efficacy of Givinostat (primary endpoint) after 3 cycles of treatment in **Part B** for PV/ET and MF patients, respectively (see [paragraph 4.6.1](#) for more details).

Frequency and percentage of patients in each response category (complete response (CR), partial response (PR), no response (NR) for PV and ET; Complete response (CR), major response, moderate response and minor response rate for MF) will be presented at each time point. In order to evaluate the response rate, subjects who discontinued prematurely the study for any reason (AE, consent withdrawal, lost to follow up) will be defined as 'Non Responder'. Other missing data will not be replaced, if not otherwise specified.

In addition, the following primary safety parameters will be evaluated in **Part B after 3 cycles of treatment** (i.e. at the end of Cycles 3, or including data related to Cycles 1, 2 and 3) based on SAF:

- Number of patients experiencing adverse events.
- Type, incidence, and severity of treatment-related adverse events, graded according to Common Terminology Criteria for Adverse Events (CTCAE v. 4.03, 14th June 2010).

AEs will be coded using MedDRA dictionary (using the most updated version). Adverse events (AEs) will be reported on a per subject basis. If a patient has more than one AE for a treatment that coded to the same preferred term (PT), the patient will be counted only once for that preferred term. Similarly, if a patient has more than one AE for a treatment within a system organ class (SOC) category, the patient will be counted only once in that system organ class category. A patient with multiple CTCAE grades for an AE will be summarized under the maximum CTCAE grade recorded for the event.

Any Adverse Events which started at or after the first administration of study treatment will be considered a treatment Emergent Adverse Event (TEAE). If the start date is missing for an AE, the AE will be considered to be treatment emergent.

TEAE included in this analysis are defined as those starting prior to the date of the first administration of Cycle 4 and include those started prior but continued during the subsequent cycle.

An overview of AEs including the number of subjects with at least one AE, at least one TEAE, at least one drug-related TEAE, at least one serious TEAE, any SAE, any AE leading to death, any TEAE leading to death, any TEAE leading to drug discontinuation, at least one grade ≥ 3 TEAE, will be presented. The following AE frequency tables will be also provided:

- incidence of TEAEs by primary SOC and PT;
- incidence of drug-related TEAEs by primary SOC and PT;
- incidence of TEAEs by maximum severity, primary SOC and PT;
- incidence of TEAEs by strongest relationship, maximum severity, primary SOC and PT;
- incidence of TESAEs by primary SOC and PT;
- incidence of TEAEs leading to study drug discontinuation by primary SOC and PT;
- incidence of TEAEs leading to dose modification by primary SOC and PT.

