4.5.4.2.1 Pre-treatment evaluations (up to 4 weeks: -28 to Day -1)

The following procedures will be performed at the pre-treatment visit of **Part B** as reported below:

- Informed consent signing;
- Demographic data (race, sex and date of birth);
- Adverse event recording;
- Concomitant medications (drugs);
- Significant non-drug therapies (e.g. phlebotomies, transfusions) recording (*if applicable*);
- Medical history;
- Physical examination, vital signs (blood pressure, pulse rate, respiratory rate), height, weight, body temperature and ECOG performance status;
- Pregnancy test (*if indicated*);
- Blood chemistry: ALT/SGPT, AST/SGOT, ALP, total bilirubin, LDH, creatinine, BUN or Urea (as per site-specific clinical practice; see [Appendix F](#) to convert Urea to BUN), glucose, Na, K, Ca, Cl, Mg, albumin, eGFR determination (according with the Mayo Clinic Quadratic Equation);
- ECG, QTc determination (according with Bazett's correction formula);
- Urinalysis: pH, specific gravity, protein, glucose;
- Haematology: RBC count, HCT, Hb, MCV, MCH, MCHC, WBC count (full and differential), PLT count;
- Spleen evaluation by MRI or CT scan;
- Collection of a blood sample for the quantitative RT-PCR evaluation of JAK2^{V617F} mutational status on peripheral blood (PB) granulocyte;
- Assessment of disease-related symptoms using the MPN-SAF QOL Questionnaire [24, 32];
- Bone marrow histological evaluation, in patients who have consented to this optional exploratory research, who haven't this assessment in the month before the 1 month before the study start (i.e the signature of the Informed Consent

Form, and that have not any medical contraindication to bone marrow sampling as judged by the Investigator);

- Request of enrolment and receipt of patient ID.

Patients must have an Eastern Cooperative Oncology Group (ECOG) performance status [28] ≤ 2 within 7 days of initiating study drug.

The pregnancy test (if indicated) has to be performed within 72 hours before the first Givinostat dose. The test can be performed by urine or serum pregnancy test. In case of a borderline-positive urine pregnancy test, this must be confirmed with a serum pregnancy test and the result recorded in the CRF. Pre-treatment evaluations will be performed at one or more clinic visit to determine eligibility for the study. Pre-treatment evaluations must be performed up to 4 weeks before the treatment start within ± 7 days.

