5.1 Definitions

5.1.1 Adverse Event (AE)

An Adverse Event is “any untoward medical occurrence in a patient or clinical investigation subject administered a pharmaceutical product and which does not necessarily have a causal relationship with this treatment” (ICH E2A).

AEs include:

- Onset of any clinical sign or symptom;
- Worsening (change in nature, severity or frequency) of conditions present at the start of the trial;
- Patient deterioration due to the primary illness;
- Intercurrent illnesses;
- Drug interactions;
- Events related or possibly related to concomitant medications;
- Abnormal laboratory values, as well as significant shifts from baseline within the range of normal, which the investigator considers to be clinically significant.

An AE can therefore be any unfavourable and unintended sign (including an abnormal laboratory finding, for example), symptom, or disease temporally associated with the use of a medicinal product, whether or not considered related to the medicinal product.

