5.2 AE Reporting

The Investigators or their designees are requested to collect and assess any spontaneous AE reported by the patient and to question the patient about AEs and undercurrent illnesses at each visit during the treatment period and any follow-up visit performed to monitor any drug-related AE that is still ongoing beyond the last scheduled visit until recovery. The questioning of patients regarding AEs is generalized such as “*How have you been feeling since your last visit?*” Any AE occurring after a patient has signed the Informed Consent form and up to the follow-up study visit, whether volunteered by the patient, discovered during general questioning by the Investigators or detected through physical examination, laboratory test or other means, will be recorded on the specific section of the CRF. Each AE will be described by:

- *the seriousness;*
- *the duration (start and end dates);*
- *the severity;*
- *the relationship with the IMP;*
- *the action taken.*

The severity of AE should be assessed and graded according to the most recently published NCI Common Terminology Criteria for AE (CTCAE v. 4.03, 14th June 2010).

The relationship with the IMP should be assessed as:

- *related to IMP;*
- *not related to IMP;*
- *unknown.*

The assessment of the relationship of an adverse event with the administration of IMP is a clinical decision based on all available information at the time of the completion of the CRF.

An assessment of “*Not related*” would include the existence of a clear alternative explanation, or non-plausibility.

An assessment of “*Related*” indicates that there is a reasonable suspicion that the adverse event is associated with the use of the IMP.

An assessment “*Unknown*” indicates there is not a reasonable suspicion that the adverse event is associated with the use of the IMP and at the same time there is not the existence of a clear alternative explanation or non-plausibility. In this case, Investigator has to collect all possible information in order to assess the relationship with the IMP, particularly in case of Serious Adverse Events.

Factors to be considered in assessing the relationship of the adverse event to study drug include:

- *The temporal sequence from IMP administration;*
- *The recovery on discontinuation and recurrence on reintroduction;*
- *The concomitant diseases;*

- *The evolution of the treated disease;*
- *The concomitant medication;*
- *The pharmacology and pharmacokinetics of the IMP;*

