5.2.2 Baseline medical conditions

Medical conditions present at the screening visit, that do not worsen in severity or frequency during the study are defined as baseline medical conditions and are not AEs. These medical conditions should be adequately documented on the appropriate page of the CRF, i.e. the medical history page. However, medical conditions present at the initial study visit that worsen in severity or frequency during the study should be recorded and reported as AEs.

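### The TEAE definition uses onset date alone, so an AE that opens between consent and first dose, stays in one record and worsens on Givinostat is missing from all seven AE frequency tables

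*Protocol*

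**What the plan says.** For Part B primary safety, section 6.2.5.2 of the protocol states: "Any Adverse Events which started at or after the first administration of study treatment will be considered a treatment Emergent Adverse Event (TEAE". One supplement deals with unknown onset: "If the start date is missing for an AE, the AE will be considered to be treatment emergent". The limit of the three-cycle analysis is also set by onset: "TEAE included in this analysis are defined as those starting prior to the date of the first administration of Cycle 4". Sections 6.2.5.1 (Part A) and 6.2.6.2 (Part B, six cycles) repeat the definition. None of the three mentions worsening.

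Collection starts earlier than the definition does. Section 5.2 records "Any AE occurring after a patient has signed the Informed Consent form and up to the follow-up study visit". AE recording is scheduled at the pre-treatment visit and again before dosing on Day 1. For the length of that interval in Part B, section 4.5.4.2.1 says: "Pre-treatment evaluations must be performed up to 4 weeks before the treatment start within ± 7 days".

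On worsening, section 5.1.1 lists among AEs "Worsening (change in nature, severity or frequency) of conditions present at the start of the trial", and section 5.2.2 adds: "However, medical conditions present at the initial study visit that worsen in severity or frequency during the study should be recorded and reported as AEs". For tabulation, sections 6.2.5.1 and 6.2.5.2 say: "A patient with multiple CTCAE grades for an AE will be summarized under the maximum CTCAE grade recorded for the event".

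**The concern.** One primary safety parameter in both parts concerns the kinds, frequency and grade of treatment-related AEs. Among the listed AE outputs, only the TEAE tables show term, grade and relationship to drug. If a mild complaint opens during screening and becomes severe and drug-related on treatment, a definition that looks only at the first start date leaves the on-drug deterioration out of those tables.

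The study has no control arm, so no comparison could reveal the omission. The definition is also uneven. An AE with no start date is counted as treatment-emergent, while one known to have worsened on drug is not. Two patients with the same deterioration on drug can be tabulated differently because the mild phase began before the initial visit in one and shortly after it in the other.

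**Working it through.** No stated figure is at issue. The check applies the definition to a test event and counts the outputs it reaches.

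1. **Interval before first dose.** Collection runs from consent. The pre-treatment period is up to 4 weeks with a 7-day window, so on the widest reading 28 + 7 = 35 days.

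2. **Test event.** Onset on Day -5 at Grade 1; Grade 3 and judged drug-related by Day 10. The condition for a TEAE is start day ≥ 1.
   - One record, start Day -5: -5 ≥ 1 is false, so it is not a TEAE.
   - New record at the worsening, start Day 10: 10 ≥ 1 is true, so it is a TEAE. It also precedes Cycle 4 and so enters the three-cycle analysis.

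3. **Outputs listed in 6.2.5.2** (6.2.5.1 and 6.2.6.2 list the same ones).
   - Frequency tables: seven, all restricted to TEAEs or serious TEAEs. The single-record event appears in 0 of 7.
   - Overview: nine rows. Six are restricted to TEAEs: any, drug-related, serious, fatal, leading to drug discontinuation, and Grade 3 or higher. The event appears in none of these.
   - The other 9 - 6 = 3 rows are not restricted: at least one AE, any SAE, and any AE leading to death. The patient counts in the first, and in the other two if the event qualifies.

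4. **Does the protocol decide between one record and two?**
   - Section 5.1.1 makes worsening an AE, but for conditions present when the trial starts. Section 4.5.3.6 equates study start with signing consent, so a complaint that arises after consent does not plainly qualify.
   - Section 5.2.2 covers conditions present at the initial or screening visit.
   - Section 4.5.2 sends examination findings present before study drug to the history sections of the CRF, and later findings that meet the AE definition to the AE section.
   - Section 4.7 sends findings already present at screening to the history sections, and findings arising after enrolment to the AE section.
   - Section 5.2 records every AE from consent, with start date, end date and severity, and does not say what to do when the grade changes.
   - The maximum-grade sentence shows that one AE may carry several grades. It does not say how records are kept.

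   Taken together, these leave open an AE that begins after consent and before Day 1.

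5. **Unit of size.** One patient among the 28 planned for Part B is 1/28 = 3.6 percentage points. The documents do not say how many patients have an AE open at first dose, or how many of those worsen.

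**The case against.** The strongest reply is that the loss depends on a recording convention the protocol never states. The maximum-grade sentence sits among per-patient counting rules and fits several records as well as one. If sites enter a worsening as a new AE, the present definition already captures it. Sections 5.1.1, 5.2.2, 4.5.2 and 4.7 point that way for much of the screening period, particularly as screening may take more than one visit. This stands: the loss is conditional, and the uncovered interval may be shorter than four to five weeks. But none of these sections settles the case in question, and section 5.2 puts such events in the AE record from consent.

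A second reply is that section 6.2 calls its methods an outline and leaves full detail to the SAP, while CRF completion has its own guidelines. Those documents could well govern how grade changes are recorded. The definition of a TEAE is different: the protocol states it in full, three times, so the SAP would inherit it.

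A third reply is that other outputs would show the deterioration. Section 6.2.8 gives laboratory, ECG and physical-examination shift tables, and section 6.2.3 summarises reasons for discontinuation. Thrombocytopenia is unlikely to be open before dosing, because entry requires platelets above 400 x 10^9/L. This stands for laboratory events. It does not help with symptoms. Section 1.4 names gastrointestinal toxicity among the most common AEs, and the Amendment 2 rationale reports dyspepsia as the one DLT among the six patients at Dose Level 1. A complaint of that kind can begin mildly before dosing and leaves no trace in a laboratory shift table.

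**Conclusion.** The point holds in conditional form. Under the stated definition, an AE that opens between consent and first dose, is kept as one record and worsens on Givinostat is excluded from seven of seven frequency tables and six of nine overview rows. This rests on the worsening staying in the original record, which the protocol neither requires nor rules out.

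Three stronger readings are not supported.

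- A reader might infer that such an event vanishes from every primary safety output. Three overview rows are not limited to TEAEs and would or could count the patient.
- A reader might infer that the primary safety endpoint as a whole is biased low. Its first parameter is the number of patients with AEs, which is not limited to TEAEs. The exposure is in the outputs by term, grade and relationship.
- A reader might put a patient count on it. Assuming that 10-30% of 28 patients have an AE open at first dose and 20-40% of those worsen gives 28 x 0.10 x 0.20 = 0.56 to 28 x 0.30 x 0.40 = 3.36 patients. Neither share is in the documents, so this is an illustration only. Nor do the documents show that stopping earlier treatment makes new complaints likely in this interval: washout may precede consent, and phlebotomy is required only for HCT of 45% or more.

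The size therefore cannot be derived. MTD determination rests on Cycle 1 DLTs, and neither the sample size nor the two-stage efficacy rule uses TEAEs, so all three are untouched.

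**What to change.** In sections 6.2.5.1, 6.2.5.2 and 6.2.6.2, define a TEAE as an AE that starts on or after first dose, or that starts before it and increases in CTCAE grade or becomes serious on or after first dose. Date the second kind by the worsening, so that it falls in the correct period (Cycles 1-3 or 4-6), and tabulate it at its maximum post-dose grade.

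The alternative is to keep the definition and state in section 5.2 that each worsening after first dose of an AE already open is entered as a new AE record with its own start date.

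The first option costs one sentence in three places and needs the CRF to hold the date of each grade change. The second moves that work to the sites and the CRF completion guidelines. Under either, TEAE counts may rise slightly.

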6.2.6 Secondary Efficacy and Safety evaluation

6.2.6.1 Part A

The following secondary efficacy parameters will be evaluated in **Part A after 3 and 6 cycles of treatment** (i.e. at the end of Cycles 3 and 6, respectively) based on ITT and PP:

- Preliminary efficacy of Givinostat (secondary endpoint) for PV/ET and MF patients, respectively (see [paragraph 4.6.1](#) for more details):
 - **For PV and ET (if any):** Complete response (CR) and partial response (PR) rate according to the clinico-haematological ELN response criteria [21] (see [paragraph 4.6.1](#));
 - **For MF (if any):** Complete response (CR), major response, moderate response and minor response rate according to the EUMNET response criteria (see [paragraph 4.6.1](#)).

Note that only in case the enrolment in **Part A** is slow (i.e. **< 5 patients enrolled in 3 months**, the eligibility for this part of the study may be expanded to all patients with cMPN.

Frequency and percentage of patients in each response category (complete response (CR), partial response (PR), no response (NR) for PV and ET; Complete response (CR), major response, moderate response and minor response rate for MF) will be presented at each time point. In order to evaluate the response rate, subjects who discontinued prematurely the study for any reason (AE, consent withdrawal, lost to follow up) will be

defined as ‘Non Responder’. Other missing data will not be replaced, if not otherwise specified.

The following secondary parameter will be evaluated in **Part A** based on PK analysis set:

- Individual Givinostat concentrations tabulated by dose cohort along with descriptive statistics.

The PK analysis will be conducted on the PK population.

Plasma concentrations from **Part A** will be listed and tabulated by dose and time point for all patients and time points with at least 1 PK assessment.

Descriptive statistics for all PK parameters for **Part A** will be calculated. These tables will include number of observations, mean, standard deviation, median, minimum and maximum and additionally the geometric mean and coefficient of variation (not for time to maximum plasma concentration).

6.2.6.2 Part B

The following secondary efficacy parameter will be evaluated in **Part B after 6 cycles of treatment** (i.e. at the end of Cycle 6) based on ITT and PP:

- Preliminary effectiveness of Givinostat (secondary endpoint) after 6 cycles of treatment in **Part B** for PV/ET and MF patients, respectively (see [paragraph 4.6.1](#) for more details):
 - **For PV and ET (if any):** Complete response (CR) and partial response (PR) rate according to the clinico-haematological ELN response criteria [21] (see [paragraph 4.6.1](#));
 - **For MF (if any):** Complete response (CR), major response, moderate response and minor response rate according to the EUMNET response criteria (see [paragraph 4.6.1](#)).

Note that only in case the enrolment in **Part A** is slow (i.e. < 5 patients enrolled in 3 months), the eligibility for this part of the study may be expanded to all patients with cMPN.

Frequency and percentage of patients in each response category (complete response (CR), partial response (PR), no response (NR) for PV and ET; Complete response (CR), major response, moderate response and minor response rate for MF) will be presented at each time point. In order to evaluate the response rate, subjects who discontinued prematurely the study for any reason (AE, consent withdrawal, lost to follow up) will be defined as ‘Non Responder’. Other missing data will not be replaced, if not otherwise specified.

The following secondary safety parameter will be evaluated in **Part B after 6 cycles of treatment** (i.e. at the end of Cycles 6, or including data related to Cycles 4, 5 and 6) based on safety population:

- Number of patients experiencing adverse events.
- Type, incidence, and severity of treatment-related adverse events, graded according to Common Terminology Criteria for Adverse Events (CTCAE v. 4.03, 14th June 2010).

AEs will be coded using MedDRA dictionary (using the most updated version). Adverse events (AEs) will be reported on a per subject basis. If a patient has more than one AE for a treatment that coded to the same preferred term (PT), the patient will be counted only once for that preferred term. Similarly, if a patient has more than one AE for a treatment within a system organ class (SOC) category, the patient will be counted only once in that system organ class category. A patient with multiple CTCAE grades for an AE will be summarized under the maximum CTCAE grade recorded for the event.

